Results Part 2: Validation of FAQ-Quotient. Out of the 89 PD-MCI patients, 32.6% presented with FAQ_Q values >1 , while 67.4% had an FAQ_Q ≤ 1 . The frequency of males was comparable between both PD-MCI subgroups (FAQ_{Q>1} 65.5%, FAQ_{Q≤1} 63.3%; $p=0.99$). Logistic regression analyses showed that patients defined as PD-MCI FAQ_{Q>1} were more impaired in tests assessing attention/working memory ($p=0.033$) and language performance ($p = 0.019$) than the PD-MCI FAQ_{Q≤1} group, while motor symptom severity revealed no significant difference between groups ($p=0.095$). Therefore, subgrouping PD-MCI patients according to the cognitive and motor performance in the FAQ is suitable for differentiating between different levels of severity for cognitive impairment in PD.

4. Objectives of the study

The FAQ is an economic and easy to apply ADL scale. Items of the FAQ have been previously published [25, 26]; details of the construction of our FAQ parameters are currently under review for publication and will also be available without additional costs.

The aim of our project is to evaluate whether the combination of PD-MCI along with cognitive-driven ADL impairment predicts the future development of PDD and might be able to differentiate between those PD-MCI patients with a high risk for the development of PDD from those with stable PD-MCI. The identification of a high-risk group for PDD among those with PD-MCI is essential for upcoming clinical trials targeting cognitive impairment in its earliest stages.

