4.1. Hypothesis and research questions

Based on previous reports and preliminary results, we hypothesize that PD-MCI patients with a more pronounced cognitive-driven ADL impairment (FAQ_{Q>1}) are at higher risk for conversion to PDD than PD-MCI patients with ADL impairment primarily related to motor function (FAQ_{Q≤1}).

1. Stratification of subgroups according to their baseline cognitive status (PD-MCI vs. normal cognition, PD-CN) and ADL function (cognitive-driven (FAQ_{Q>1}) vs. motor-driven (FAQ_{Q≤1})).
2. Defining progression of ADL impairment over time.
Aim 2.1: Evaluation of stability and/or progression of ADL status between baseline and follow-up (FAQ_{Q>1} vs. FAQ_{Q≤1}).
3. Evaluation of the interaction between cognition and ADL function over time.
Aim 3.1: Evaluation of conversion rates to PD-MCI and PDD according to baseline ADL status (FAQ_{Q>1} vs. FAQ_{Q≤1}).
Aim 3.2: Prediction of PD-MCI (among PD-CN) and PDD according to baseline ADL, cognitive, genetic, and biomarker profiles in blood and CSF.
Aim 3.3: Progression of decline in cognition and ADL function in relation to Amyloid and Tau burden.

5. Study duration

Total duration of the study is 2 ½ years.

6. Study population

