6.1. Study population

Between March 30th, 2014 and December 31th, 2017, we recruited a large cohort of 262 PD patients within the frame of the “Amyloid-Beta in cerebrospinal fluid as a risk factor for cognitive dysfunction in Parkinson’s Disease” (ABC-PD, ethic protocol 686/2013B01) study. Of the total baseline sample, 43% were diagnosed with PD-MCI (63% males, mean age of 67.2 ± 7.7 years) whereas 57% had normal cognitive function (61% males, mean age of 65.4 ± 8.7 years). Mean disease duration of the total sample was 5.1 ± 3.9 years.

We propose to follow-up the already existing ABC-PD cohort described above with a longitudinal assessment including neuropsychological in-depth endophenotyping and CSF biomarker analyses. The estimated mean follow-up interval is 46.6 ± 6.6 months.

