6.3. Recruitment

Participants of the already recruited ABC-PD cross-sectional cohort (ethic protocol 686/2013B01) will be asked to participate in the follow-up assessment. Patients who did not agree to participate in a longitudinal study or who have asked not to be contacted after the first cross-sectional assessment will not be contacted again. A drop-out rate of 20% is expected for follow-up retention. Therefore, investigation of 209 patients will be conducted between August 2018 and April 2020. During the executive project phase, three patients will be assessed weekly (~12 per month). Patients will be contacted either via phone or in written form. Reason for drop-outs will be registered for data analysis.

7. Statistics and Sample size estimation

The relative risk as well as the positive and negative Likelihood Ratios according to baseline group status for conversion to PD-MCI or PDD will be calculated.

1. Between-group differences will be conducted using either a Student's t-test, analyses of variance (ANOVA), or covariance analyses.
2. For longitudinal within-group analyses of cognitive and ADL progression, we will use either paired t-tests or repeated ANOVA models. Additionally, Kaplan Mayer survival curves and Cox proportional hazard models stratified by the individual group status (e.g. PD-MCI with and without cognitive-driven ADL impairment) will be applied to estimate the time period to PD-MCI or PDD conversion.
3. Associations between serum and CSF markers along with ADL and cognitive data will be carried out using multivariate regression analyses in order to evaluate the type of biomarker that best reflects the biological impact on phenotype and progression.

Reports on conversion rates of new-onset PD-MCI and PDD are highly variable between studies [5]. At a mean follow-up interval of around four years, the frequency of PDD in large

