PD cohorts is estimated to vary between 13% [7] and 28% [27], resulting in 27 to 58 patients with PDD in the present cohort at follow-up. New-onset PD-MCI is expected to be higher, with around 49 (36%) [6] to 107 (78%) cases in our cohort [27]. Of all PD-MCI patients, one-third are classified as having cognitive-driven compared to motor-driven ADL impairment, resulting in at least 16 to 35 new-onset PD-MCI patients classified as FAQ_{Q>1} [24]. These estimates resemble the sample size of our preliminary data described above, for which between-group differences have been statistically verified. Therefore, we conclude that moderate to strong effects can be detected with 80% power in two-group comparisons.

8. Assessments

Table 1: Overview of assessments

Assessment of PD patients	Time
Explanation of the study requirements	10 min
Demographics & lifestyle	
Age, gender, education, occupation, family history of neurodegenerative diseases, smoking/drinking behavior, height & weight	5 min
Neurological Assessments:	
Medication intake, concomitant diseases, and procedures	10 min
Unified Parkinson's Disease Rating Scale (UPDRS) Parts III-IV, Hoehn & Yahr Stage	15 min
Olfactory testing using the Sniffin Sticks 12 odor test	3 min
PD Non-Motor Symptom Scale, subscales 1-5 (PD-NMS-S)	5 min
Unified Multiple System Atrophy Rating Scale (UMSARS) I: History of autonomic symptoms	2 min
Cognitive test battery:	
History and self-awareness of cognitive deficits	5 min
Montreal Cognition Assessment (MoCA)	10 min
Mini Mental State Examination (MMSE)	5 min
Consortium to Establish a Registry for Alzheimer's Disease (CERAD-Plus, German Version)	25 min
Trail Making Test Parts A and B	10 min
Fragmented Words (Subtest of the Leistungsprüfssystem für 50- bis 90-Jährige, LPS 50+)	5 min
Digit-Symbol Test (Subtest of the Wechsler Intelligenztest für Erwachsene, WIE)	5 min
Similarities (Subtest of the WIE)	5 min
Letter-Number Sequencing (Subtest of the WIE)	5 min
Demenz Apraxie Test (DAT)	5 min
Pill-Questionnaire	5 min
Patient Questionnaires (can be filled out at home):	
Parkinson's Disease-Non-motor Symptoms Questionnaire (PD-NMS-Q)	3 min
Beck Depression Inventory – II (BDI-II)	5 min
Geriatric Depression Scale (GDS)	2 min
Beck-Anxiety-Inventory (BAI)	2 min
Functional Activities Questionnaire (FAQ)	2 min
Parkinson's Disease Activities of Daily Living Scale	1 min
Parkinson's disease Questionnaire (PDQ-39)	5 min
Freezing of Gait Questionnaire (FOG)	1 min
Epworth Sleepiness Scale (ESS)	2 min

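### Section 7's only FAQ_Q>1 count (16–35) does not size the baseline FAQ_Q groups that the hypothesis and Aim 3.1 compare; the baseline PD-MCI groups are about 29 vs 61, enough for strong effects but not for d = 0.5

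*Combined protocol and SAP*

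**What the plan says.** Section 7 (Statistics and Sample size estimation) expects 49 to 107 new-onset PD-MCI cases. It then says of PD-MCI patients that "one-third are classified as having cognitive-driven compared to motor-driven ADL impairment, resulting in at least 16 to 35 new-onset PD-MCI patients classified as" FAQ_Q>1. This is the only FAQ_Q>1 count in the section. Because the estimates resemble the preliminary sample, the section concludes that moderate to strong effects can be detected with 80% power in two-group comparisons. It gives no numeric effect size, significance level or sidedness.

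The one-third matches Section 3.2: "Out of the 89 PD-MCI patients, 32.6% presented with FAQ_Q values" above 1. Those 89 patients had PD-MCI when the cohort was first assessed.

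Section 4.1 groups patients by baseline status. The hypothesis compares PD-MCI patients with FAQ_Q>1 and FAQ_Q≤1 for conversion to PDD. Aim 3.1 is "Evaluation of conversion rates to PD-MCI and PDD according to baseline ADL status". Section 7 likewise plans relative risks and likelihood ratios by baseline group, plus Cox models, for conversion to PD-MCI or PDD.

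**The concern.** New-onset PD-MCI patients are, by definition, people who were cognitively normal at baseline (PD-CN); Aim 3.2 says so. To size a comparison of conversion to PD-MCI by baseline FAQ_Q, one needs the FAQ_Q>1 share among PD-CN patients. To size the main hypothesis, one needs the FAQ_Q split of the baseline PD-MCI patients who return. Section 7 gives neither. It multiplies incident cases by a share taken from prevalent cases, which yields a subset of people defined by an outcome rather than a group to be compared.

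This matters because the count is the step from the expected numbers to the power statement. If that step does not describe the comparison groups, the reader cannot tell what the study can detect. A null result on conversion could then be read as evidence of no association when power was modest.

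**Working it through.** **Inputs.** Cohort: "we recruited a large cohort of 262 PD patients" (Section 6.1). Baseline status: "Of the total baseline sample, 43% were diagnosed with PD-MCI", "whereas 57% had normal cognitive function" (Section 6.1). Retention: "A drop-out rate of 20% is expected for follow-up retention"; "investigation of 209 patients will be conducted between August 2018 and April 2020" (Section 6.3). FAQ_Q>1 share in baseline PD-MCI: 32.6% of 89 (Section 3.2). New-onset PD-MCI: 49 to 107 (Section 7), taken as given. Background conversion from PD-MCI to dementia: 26% to 39.1% (Section 3.1). Assumed here because the plan is silent: two-sided 5% level and equal drop-out across groups.

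**1. Reproduce the plan's count.** 0.326 × 49 = 16.0 and 0.326 × 107 = 34.9, i.e. 16 to 35. In the development sample, 0.326 × 89 = 29, leaving 60.

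**2. Baseline PD-MCI groups at follow-up (main hypothesis, PDD outcome).** 0.43 × 209 = 90; 0.326 × 90 = 29 with FAQ_Q>1; 90 − 29 = 61 with FAQ_Q≤1.

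**3. Power for a difference in means.** Two-sample t-test. The normal approximation for the detectable difference is d = (1.96 + 0.84) × √(1/n₁ + 1/n₂); for 29 vs 61 this gives 0.63, and the t-distribution gives 0.64. The first and last rows below split the plan's own new-onset cases (49 − 16 = 33; 107 − 35 = 72).

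| Groups | Power at d = 0.5 | Power at d = 0.8 | d at 80% power |
|---|---|---|---|
| 16 vs 33 | 36% | 73% | 0.87 |
| 29 vs 61 | 59% | 94% | 0.64 |
| 35 vs 72 | 67% | 97% | 0.58 |

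None of these reaches 80% at d = 0.5.

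**4. The same groups on the conversion scale.** With 90 patients and 26% to 39.1% converting, PDD events number about 23 to 35. By Schoenfeld's formula, the hazard ratio detectable with 80% power is exp[(1.96 + 0.84) / √(events × 0.326 × 0.674)]. This is about 3.4 at 26% and 2.7 at 39.1%. Power at a hazard ratio of 2 is about 35% to 49%. The conversion range is the protocol's background figure, carried over to this follow-up as an assumption.

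**5. Baseline PD-CN groups (PD-MCI outcome).** 0.57 × 209 = 119 patients. The FAQ_Q>1 share is not given, although the development sample held 216 − 89 = 127 such patients. Assumed shares show how much depends on it:

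| Assumed share | Groups | Power at d = 0.5 | d at 80% power |
|---|---|---|---|
| 10% | 12 vs 107 | 37% | 0.86 |
| 20% | 24 vs 95 | 58% | 0.65 |
| 32.6% | 39 vs 80 | 72% | 0.55 |

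**The case against.** The strongest reply is that the sentence most naturally describes FAQ_Q status at follow-up. The patients counted are PD-MCI by then, and the FAQ is given again at that visit (Table 1). Applying a PD-MCI share to PD-MCI patients is like for like, if untested. Such a count could serve Aim 2.1 or a cross-sectional contrast, and the power sentence speaks only of two-group comparisons. This stands: the multiplication is not wrong on that reading. But FAQ_Q status is then measured at the same visit as the PD-MCI outcome, with no later visit planned at which PDD could be seen. The count still sizes no conversion comparison by baseline status.

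A second reply is that the main hypothesis is unharmed: 29 vs 61 lies inside 16–35 and is almost the preliminary 29 vs 60. This also stands. A reader might infer that the plan overstates the FAQ_Q>1 group for its main question; its own figures do not show that. Resemblance to the preliminary sample nevertheless does not establish 80% power for moderate effects, as step 3 shows.

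A reader might also infer that 16–35 is several-fold too high, because cognitively normal patients should rarely have FAQ_Q>1. The documents do not support this. They report no PD-CN share, and the link between FAQ_Q>1 and poorer test performance in Section 3.2 is within PD-MCI only. Holding 49–107 fixed and assuming no association with conversion, a three-fold excess would need a share of about 11% or less (0.326 / 3), a figure found nowhere in the plan.

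**Conclusion.** The point holds, and it goes beyond a missing table entry. The one FAQ_Q>1 count behind the power statement does not size the groups that the hypothesis and Aim 3.1 compare. On every FAQ_Q split of PD-MCI patients that the documents support, power at d = 0.5 is about 36% to 67%. For the main-hypothesis groups (about 29 vs 61), power is about 59% at d = 0.5 and 94% at d = 0.8. The 80% statement is therefore good for strong effects but not for moderate ones, if moderate means d = 0.5; the plan does not define the word.

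For conversion to PD-MCI, neither the size nor the direction of any error can be shown, so *at least* is unsupported rather than demonstrably wrong. These conclusions rest on a two-sided 5% test, equal drop-out by group, and a 32.6% share among the PD-MCI patients who return.

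**What to change.** In Section 7:

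- For the PDD outcome, replace the 16–35 step with the baseline PD-MCI group sizes expected at follow-up, about 29 vs 61, and the PDD events expected in each.
- For the PD-MCI outcome, tabulate the FAQ_Q>1 share in the 127 PD-CN patients of the development sample. Apply it to the roughly 119 expected PD-CN attendees, and state both group sizes and the expected converters in each.
- Delete *at least*.
- State the significance level and sidedness, and give the effect detectable with 80% power for each comparison. For conversion, use the risk-ratio or hazard-ratio scale that the planned analyses report. For the PDD comparison this is a hazard ratio of about 2.7 to 3.4 under the assumptions above.

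The cost is one tabulation of data already held and a few sentences. The detectable effects will look less favourable than the present wording. Nothing changes for patients or procedures.

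### The 80% power for moderate to strong effects has no calculation behind it; for PDD conversion by baseline FAQ_Q group (about 29 vs 61) it needs a risk ratio of about 2.6–2.0 or a hazard ratio of about 3.5–2.75

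*Combined protocol and SAP*

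**What the plan says.** Section 4.1 hypothesises that PD-MCI patients with FAQ_Q>1 convert to PDD more often than PD-MCI patients with FAQ_Q≤1. For conversion, Section 7 plans "The relative risk as well as the positive and negative Likelihood Ratios according to baseline group status for conversion to PD-MCI or PDD", and "Cox proportional hazard models stratified by the individual group status (e.g. PD-MCI with and without cognitive-driven ADL impairment) will be applied". Group differences may also be tested by t-test, "analyses of variance (ANOVA), or covariance analyses".

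The sample size text in Section 7 projects PDD cases ("resulting in 27 to 58 patients with PDD in the present cohort at follow-up") and new-onset PD-MCI ("New-onset PD-MCI is expected to be higher, with around 49 (36%) [6] to 107 (78%) cases in our cohort [27"). It applies the FAQ_Q split to the latter, "resulting in at least 16 to 35 new-onset PD-MCI patients classified as FAQ_{Q>1} [24".

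It then argues: "These estimates resemble the sample size of our preliminary data described above, for which between-group differences have been statistically verified". The conclusion follows at once: "Therefore, we conclude that moderate to strong effects can be detected with 80% power in two-group comparisons".

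**The concern.** This is the plan's only statement of what the study can detect, and it is worded for two-group comparisons in general. Three things are wrong with it.

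- **No inputs.** No alpha, sidedness, numeric effect size, formula or pair of group sizes is attached to the 80%.
- **The inference fails.** Significance in an earlier sample does not show 80% power at that sample size. The preliminary results in Section 3.2 are also cross-sectional differences in baseline test performance, not conversion over about four years.
- **The hypothesis comparison is not covered.** The only FAQ_Q-split counts are for new-onset PD-MCI, whereas the hypothesis concerns patients who already have PD-MCI at baseline.

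A reader therefore cannot tell what risk ratio or hazard ratio the main comparison could detect. A null result for a hazard ratio near 2 could be taken as evidence against FAQ_Q when the study would probably have missed it.

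**Working it through.** **The plan's own figures**
- Retained: 262 × 0.80 = 209.6; the plan uses 209 (Sections 6.1, 6.3).
- PDD: 209 × 13% = 27 and 209 × 28% = 58.5, given as 58. These reproduce.
- New-onset FAQ_Q>1: 49/3 = 16 and 107/3 = 35.7, given as 35. These reproduce from 49 and 107.
- The 80% cannot be reproduced, because it has no inputs.

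**The resemblance argument**
- Preliminary split: 89 PD-MCI × 32.6% = 29, so 29 vs 60, with p=0.033 and p=0.019 on two cognitive domains.
- Normal approximation, taking the observed effect as true: power = Φ(z − 1.96). For p=0.033, z = 2.13 and power is about 57%. For p=0.019, z = 2.35 and power is about 65%. Neither is 80%.

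**Group sizes for the hypothesis comparison**
- 209 × 43% = 90 PD-MCI (Section 6.1); 90 × 32.6% = 29 (Section 3.2), so 29 vs 61. This assumes equal drop-out.

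**Risk ratio** (two-sided 5%, assumed; pooled two-proportion z-test, exact binomial enumeration). Overall conversion of 26%–39.1% is from Section 3.1, which gives no interval; I assume it applies to this follow-up. Group risks: p2 = overall × 90/(29 × RR + 61), p1 = RR × p2.

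| Overall conversion | Power at RR 2.0 | RR for 80% power |
|---|---|---|
| 26% | 51% (39% vs 20%) | 2.64 (45% vs 17%) |
| 39.1% | 77% (59% vs 30%) | 2.04 (60% vs 29%) |

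**Hazard ratio** (Schoenfeld, FAQ_Q group taken as the tested term). HR for 80% = exp[(1.960 + 0.842)/√(D × q(1−q))], with q = 29/90 and q(1−q) = 0.218.
- 90 × 26% = 23 events: HR 3.49; power at HR 2.0 is 34%.
- 90 × 39.1% = 35 events: HR 2.75; power at HR 2.0 is 48%.

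**Continuous outcomes** (noncentral t, two-sided 5%; d=0.5 as moderate and d=0.8 as strong are my assumptions)

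| Contrast | d=0.5 | d=0.8 | d for 80% |
|---|---|---|---|
| Baseline PD-MCI by FAQ_Q, 29 vs 61 | 59% | 94% | 0.64 |
| New-onset PD-MCI by FAQ_Q, 16 vs 33 | 36% | 73% | 0.87 |
| New-onset PD-MCI by FAQ_Q, 35 vs 72 | 67% | 97% | 0.58 |
| Baseline PD-MCI vs PD-CN, 90 vs 119 | 94.5% | >99% | 0.39 |
| PDD vs not, 27 vs 182 | 67% | 97% | 0.58 |
| PDD vs not, 58 vs 151 | 90% | >99% | 0.44 |

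**Sensitivity, 29 vs 61 at d=0.5**
- One-sided 5%: 71%.
- Covariance analysis, d/√(1−ρ²): ρ=0.5 gives 72%, ρ=0.6 gives 78%.
- One-sided and ρ=0.5 together: 81%.
- No drop-out (37 vs 76), two-sided: 70%.

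**New-onset denominator**
- 49/0.36 = 136 and 107/0.78 = 137, so about 137 PD-CN patients are implied.
- 209 × 57% = 119 under equal drop-out, giving 119 × 36% = 43 and 119 × 78% = 93 cases.

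**The case against.** The strongest reply is that the plan never defines moderate. The detectable d of 0.64 lies between the conventional 0.5 and 0.8, so if the phrase means a band, the sentence is loose rather than false. The hypothesis is directional and covariance analyses are listed; a one-sided test with a covariate correlation of 0.5 reaches 81% at d=0.5. This stands in part: a claim of 80% for a moderate effect could be defended for a continuous outcome if such an analysis were named in advance. The plan names neither a one-sided test nor a covariate set, and this route does not supply power for the conversion comparison.

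A reader might infer that power for PDD conversion is 59%. It is not: 59% belongs to a difference in means, whereas conversion is binary or time-to-event and has to be judged by the risk ratios and hazard ratios above. Nor do the documents support saying that the sentence fails everywhere, since 90 vs 119 and 58 vs 151 both exceed 80% at d=0.5.

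A reader might also call the 137 a plain error. Section 6.1 implies 262 × 57% = 149 PD-CN patients at baseline, so 137 could be retained if drop-out were about 8% in PD-CN and about 36% in PD-MCI (72 of 113). The plan does not say this, so the figures need reconciling, but an error is not proven.

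Finally, the cohort is already recruited, so no recruitment decision turns on the sentence. That limits the consequence to how results will be read.

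**Conclusion.** The concern holds. The 80% figure is unsupported, and the argument offered for it does not establish power. For the comparison the hypothesis rests on, 80% power needs a risk ratio of about 2.6 to 2.0 or a hazard ratio of about 3.5 to 2.75; a hazard ratio of 2.0 would be detected about 34%–48% of the time. For continuous outcomes in the same groups, the strong end is met and the conventional moderate end is not.

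This rests on equal drop-out across groups, a two-sided 5% test, 26%–39.1% conversion applying to this follow-up, and d=0.5 and 0.8 as readings of moderate and strong. The plan states none of these. The lack of a calculation and the unexplained gap between 137 and 119 need no assumption about alpha or effect size, though the 119 does rest on equal drop-out.

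**What to change.** In Section 7:

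1. Delete the argument from resemblance to the preliminary sample.
2. Replace the general 80% statement with detectable effects for the hypothesis comparison. For example: with about 29 FAQ_Q>1 and 61 FAQ_Q≤1 retained baseline PD-MCI patients (equal drop-out assumed) and a two-sided 5% test, the study has 80% power for a PDD risk ratio of about 2.6 to 2.0, or a hazard ratio of about 3.5 to 2.75, if overall conversion is 26% to 39.1% (an assumption); for continuous outcomes it has 80% power for a standardised difference of about 0.64.
3. Do not state 80% power for moderate effects in FAQ_Q subgroup comparisons unless a one-sided or covariate-adjusted analysis is named in advance, with its own figures. Give other contrasts separately.
4. Reconcile the new-onset PD-MCI denominator: either correct the counts to about 43–93 of 119, or state the unequal retention that gives 137.

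The cost is protocol wording. The stated power becomes less favourable; no extra patients are needed.
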